12.0 DATA REPORTING/PROTOCOL DEVIATIONS

12.1 Data Reporting

12.1.1 Confidentiality and Storage of Records

Electronic Data Collection will be used for this protocol. The data will be stored in encrypted, password protected, secure computers that meet all HIPAA requirements. When results of this study are reported in medical journals or at meetings, identification of those taking part will not be disclosed. Medical records of subjects will be securely maintained in the strictest confidence, according to current legal requirements. They will be made available for review, as required by the FDA, HHS, or other authorized users such as the NCI, under the guidelines established by the Federal Privacy Act and rules for the protection of human subjects.

12.1.2 Subject Consent Form

At the time of registration, the original signed and dated Informed Consent form, HIPAA research authorization form, and the California Experimental Subject's Bill of Rights (for the medical record) and three copies (for the subject, the research record, and the Coordinating Center) must be available. All Institutional, NCI, Federal, and State of California requirements will be fulfilled.

12.1.3 Data Collection Forms and Submission Schedule

All data will be collected using electronic data collection, stored as indicated in [Section 12.1.1](#), and will be submitted according to the timelines indicated in Table 12.1.3.

Table 12.1.3 Data Submission Schedule

Form	Submission Timeline
Eligibility Checklist	Complete prior to registration
On Study Forms	Within 14 calendar days of registration
Baseline Assessment Forms	Within 14 calendar days of registration
Treatment Forms	Within 10 calendar days of treatment administration
Adverse Event Report Forms	For cycle 1 only, within 7 calendar days of AE assessment/notification; for all other cycles, within 10 calendar days of AE assessment/notification
Response Assessment Forms	Within 10 calendar days of the response assessment
Other Assessment Forms (concomitant medications)	Within 10 calendar days of the assessment
Off Treatment/Off Study Forms	Within 10 calendar days of end of treatment/study
Follow up/Survival Forms	Within 14 calendar days of the protocol defined follow up visit date or call

Eligibility Checklist

The Eligibility Checklist must be completed by a protocol nurse or clinical research coordinator and signed by an authorized investigator prior to registering the subject. See [Section 4.3](#) for the registration procedure.

12.2 Protocol Deviations

12.2.1 Deviation Policy

This protocol will be conducted in accordance with COH's "[Clinical Research Protocol Deviation policy](#)"...

Deviations from the written protocol that could increase patient risk or alter protocol integrity require prior IRB approval of a single subject exception (SSE) request. IRB pre-approved SSE protocol modifications are considered an amendment to the protocol and not a deviation. The submission of a deviation report is not required.

Brief interruptions and delays may occasionally be required due to travel delays, airport closure, inclement weather, family responsibilities, security alerts, government holidays, etc. This can also extend to complications of disease or unrelated medical illnesses not related to disease progression. The PI has the discretion to deviate from the protocol when necessary so long as such deviation does not threaten patient safety or protocol scientific integrity. Examples include, but are not limited to: a) dose adjustments based on excessive patient weight; b) alteration in treatment schedule due to non-availability of the research participant for treatment; c) laboratory test results which are slightly outside the protocol requirements but at levels that do not affect participant safety. These instances are considered to be deviations from the protocol. A deviation report will be submitted to the DSMC/IRB within five days.

12.2.2 Reporting of Deviations

All deviations will be reported to the COH DSMC within five days. The DSMC will forward to report to the IRB following review.

12.2.3 Resolving Disputes

The COH Investigational Drug Service (IDS) cannot release a research agent that would cause a protocol deviation without approval by the PI. Whenever the protocol is ambiguous on a key point, the IDS should rely on the PI to clarify the issue.

In situations where there is misperception or dispute regarding a protocol deviation among the persons involved in implementing the protocol, it is the responsibility of the PI to resolve the dispute and the PI may consult with the DSMC chair (or designee) to arrive at resolution.

13.0 STATISTICAL CONSIDERATIONS

13.1 Definition of Dose-Limiting Toxicity (DLT)

A dose limiting toxicity (DLT) will be defined as any of the following toxicities that are **at least possibly related** to leflunomide and occur during cycle 1:

Any toxicity or series of toxicities resulting in:

- Fewer than 21 doses during cycle 1
- Extension of Cycle 1 > 35 days

Hematologic:

- Grade 4 neutropenia (ANC <500/mm³)
- Grade 3 or 4 febrile neutropenia
- Grade 4 thrombocytopenia (<25,000/mm³)
- Grade 3 thrombocytopenia (<50,000/mm³) with bleeding

Non- Hematologic:

- Grade 4 non-hematologic toxicity, with the following exceptions:
 - Diarrhea that resolves to G3 within 48 hours
 - Vomiting that resolves to G3 within 48 hours
 - Allergic reaction/hypersensitivity, or
 - Electrolyte/metabolic toxicity corrected to <Grade 1 or baseline within 48 hours
- Grade 3 toxicity despite maximal medical therapy lasting > 7 days
- Grade 2 or higher ALT (SGPT)/AST (SGOT)/Total Bilirubin elevation lasting > 14 days.
- Grade 3 or higher elevation of ALT (SGPT)/AST (SGOT)/Total Bilirubin of any duration.

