5.2 Treatment cycle definition

The planned cycle length is 28 days. Leflunomide will be taken orally once daily. Missed or held doses will not be made up. The day count continues despite a hold in agent administration. Day 1 safety assessments must be reviewed prior to the initiation of the cycle. For a cycle to commence, the participant must be actively taking study agent. Windows for procedures are detailed in [Section 10](#).

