5.11 Supportive Care, Other Concomitant Therapy, Prohibited Medications

Concomitant medications and treatments that are permitted while on study treatment include allopurinol, anti-emetics, anti-diarrheals, FDA-approved bisphosphonates, erythropoietin, transfusions (as necessary), and palliative radiation.

Concurrent treatment with any other anti-neoplastic therapies will not be permitted while on study treatment. Concurrent administration of live vaccines will not be permitted while on study treatment.

During cycle 1 only: Transfusions are not permitted unless platelets <25,000/mm³ or platelets < 50,000/mm³ accompanied by bleeding. Growth factors are not permitted unless ANC <500/mm³.

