6.0 ANTICIPATED TOXICITIES AND DOSE DELAYS/MODIFICATIONS FOR ADVERSE EVENTS

6.1 Anticipated Toxicities

6.1.1 Leflunomide

Per the package insert for leflunomide, the expected toxicities for leflunomide follow, where the asterisk (*) signifies a common event (10%-30% of patients), unmarked items are infrequent events (1-3% of patients), a double asterisk (**) signifies a rare but possibly serious event, and a triple asterisk (***+) signifies an event that may become serious and occurs in up to 10% of patients:

Blood and lymphatic system: anemia (including iron deficiency anemia), ecchymosis, pancytopenia**, agranulocytosis**, neutropenia**, thrombocytopenia**, leukopenia**,

Cardiac: angina pectoris, migraine, palpitation, tachycardia, vasodilatation

Endocrine: diabetes mellitus, hyperthyroidism

Eye: blurred vision, cataract, conjunctivitis, eye disorder

Gastrointestinal: diarrhea*, abdominal pain, dyspepsia, nausea, vomiting, oral ulceration, anorexia, pancreatitis**, constipation, esophagitis, flatulence, gastritis, gingivitis, melena, oral moniliasis, pharyngitis, salivary gland enlarged, stomatitis (or aphthous stomatitis), tooth disorder

Hepatobiliary: cirrhosis**, hepatitis**, hepatic failure**, acute hepatic necrosis**, cholelithiasis**, cholestasis**, elevated hepatic enzymes (primarily ALT and AST)

Immune system: allergic reactions, anaphylactoid reactions**

Infections: respiratory infection*, infections (including bronchitis, rhinitis, sinusitis, pharyngitis, pneumonia, and urinary tract infections, oral or vaginal candidiasis, herpes simplex, herpes zoster, and fungal dermatitis), opportunistic and/or severe infections** including sepsis, that may be fatal (especially *Pneumocystis jiroveci* pneumonia, tuberculosis, aspergillosis)

Metabolism and nutrition: hyperglycemia, creatine phosphokinase increased, hyperlipidemia

Musculoskeletal and connective tissue: arthrosis, bone necrosis, bone pain, bursitis, muscle cramps, myalgia, tendon rupture

Neoplasms: secondary malignancy**, cyst

Nervous system: headache*, peripheral neuropathy* (including peripheral numbness, tingling, burning, severe pain, cold sensation in the distal extremities, or extremity weakness), paresthesias, taste perversion (dysgeusia), anxiety, depression, dry mouth, insomnia, neuralgia, neuritis, sleep disorder, sweating increased, vertigo, migraine

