ALT (SGPT) or AST (SGOT) >3.0 - 5.0 x ULN or TBili >1.5 - ≥ 3.0 x ULN	
First Occurrence:
 
 Hold until resolution to < 3.0 x ULN for ALT or AST or < 1.5 for TBili. Resume at pre-hold dose if resolved within 14 days. If does not resolve within 14 days, permanently discontinue study agent. 
Recurrence:
 
 Hold until resolution to < 3.0 x ULN for ALT or AST or < 1.5 for TBili. Resume at next lowest safe dose if resolved within 14 days. If does not resolve within 14 days, permanently discontinue study agent.
ALT (SGPT) or AST (SGOT) > 5.0 x ULN or TBili > 3.0 x ULN	Permanently discontinue study agent.
Electrolyte/metabolic toxicity	

Electrolyte/metabolic Grade 3	Provide support care. Maintain study agent per investigator discretion. If alteration persists despite aggressive replacement therapy, then dose reduce or permanently discontinue (per investigator discretion with PI consultation).
Electrolyte/metabolic Grade 4	Provide support care. Maintain study agent per investigator discretion. If resolves to Grade 1 or baseline within 48: for first event, maintain at pre-hold dose; for recurrent event, dose reduce or permanently discontinue (per investigator discretion with PI consultation). If does not resolve to Grade 1 or baseline within 48 hours, permanently discontinue study agent.
Other unspecified Non-Hem toxicities considered related to leflunomide	
Grade 1	Maintain study agent.
Grade 2	Maintain study agent.
Grade 3	First Occurrence: Hold until resolution to ≤ Grade 2. Resume at pre-hold dose if resolved within 7 days. If does not resolve within 7 days, permanently discontinue study agent. Recurrence: Hold until resolution to ≤ Grade 1. Resume at next lowest safe dose if resolved within 14 days. If does not resolve within 14 days, permanently discontinue study agent.
Grade 4	Permanently discontinue study agent.
Other unspecified Non-Hem Toxicities considered UNRELATED to study agent	
Other unspecified events of any grade considered unlikely to be related or not related to study agents.	Maintain treatment with study agents. Interruption of study agent or dose de-escalation is permitted if the investigator consults with the Principal Investigator to determine that this is in the best interest of the participant.

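### Section 5.11, read literally, makes red-cell transfusion in cycle 1 a deviation when platelets are adequate; as a lesser point, related grade 4 anaemia can be scored as no DLT under 13.1

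*Combined protocol and SAP*

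**What the plan says.** **Transfusion (Section 5.11).** The general list of permitted supportive care includes "erythropoietin, transfusions (as necessary), and palliative radiation". A later sentence restricts this: "During cycle 1 only: Transfusions are not permitted unless platelets" are below 25,000/mm³, or below 50,000/mm³ with bleeding. No product is named and no haemoglobin condition is given. The companion sentence ties cycle 1 growth factors to an ANC below 500/mm³.

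**DLT definition (Section 13.1).** The DLTs form a fixed list of cycle 1 events at least possibly related to leflunomide.
- Two items apply to any toxicity: fewer than 21 doses in cycle 1, and "Extension of Cycle 1 > 35 days".
- The hematologic items cover neutropenia, febrile neutropenia and thrombocytopenia.
- The grade 4 catch-all is "Grade 4 non-hematologic toxicity, with the following exceptions".
- An item for grade 3 toxicity that persists beyond 7 days despite full treatment does not itself say non-hematologic, but it stands under the Non-Hematologic heading.

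**Dose modification (Table 6.2.2).** The hematologic rows cover the same three toxicities. The residual rows for related events are headed "Other unspecified Non-Hem toxicities considered related to leflunomide". Nothing applies to anaemia.

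**Expected toxicity (Section 6.1.1).** The blood and lymphatic entry opens with "anemia (including iron deficiency anemia), ecchymosis". Neither term carries an asterisk, which places them in the 1-3% category.

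**The concern.** The two sentences in 5.11 conflict for one kind of patient: severely anaemic in cycle 1 with platelets above the thresholds. The general sentence allows red cells. The cycle 1 sentence, which is the more specific and so would normally govern, does not. A clinician who transfuses is then off protocol and must report it; one who follows the text literally would withhold or delay the transfusion.

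The DLT point concerns the count that defines the MTD, a phase I primary objective. If related grade 4 anaemia meets no item in 13.1, Table 13.3.2 treats the patient as evaluable without a DLT. One listed DLT plus one such anaemia in six patients reads as 1/6, so the next patient goes to the next higher level, or the level qualifies as the MTD. Counting both gives two DLTs, and the next patient goes down a level.

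**Working it through.** **1. What the 5.11 thresholds were for.** The platelet values (25,000/mm³, and 50,000/mm³ with bleeding) are the platelet DLT thresholds in 13.1. The growth-factor value (ANC 500/mm³) is the neutropenia DLT threshold. The sentences therefore look designed to stop supportive care from masking those two DLTs. A platelet trigger makes sense only for platelet products; read literally, it would allow red cells because platelets are low and refuse them because platelets are adequate. The intent is clear, but the word used covers all transfusions.

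**2. The plan's dose threshold.** 0.75 × 28 = 21 doses, which agrees with the 75% evaluability rule in 13.2. A patient who takes 21 to 28 doses is evaluable and does not meet the dose-count item.

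**3. How long a hold escapes both any-toxicity items.** Assume one continuous hold of *h* days starting on day *s*, with no other missed dose. Section 5.2 says "For a cycle to commence, the participant must be actively taking study agent", so cycle 2 starts on day 29 or when dosing resumes, whichever is later.
- Doses in days 1-28 = 28 − min(*h*, 29 − *s*), which must be at least 21.
- Cycle 1 length = max(28, *s* + *h* − 1), which must be at most 35.

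| Hold starts on day | Longest hold meeting neither item (days) |
|---|---|
| 4 to 21 | 7 |
| 22 | 14 |
| 23, 24, 25, 26, 27, 28 | 13, 12, 11, 10, 9, 8 |
| 29 | 7 |

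Examples: a 7-day hold begun at the Day 14 blood count leaves 28 − 7 = 21 doses and a 28-day cycle. A 7-day hold begun at the cycle 2 Day 1 check leaves 28 doses and a 29 + 7 − 1 = 35-day cycle. Neither is a DLT. A hold longer than 7 days begun on days 4 to 21 does count. An investigator who keeps dosing triggers nothing, and no rule requires a hold.

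**4. Effect on escalation (illustration).** A level clears with 0/3 DLTs, or with 1/3 followed by 0/3:

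P(clear) = (1−p)³ + 3p(1−p)² × (1−p)³, where p is the counted DLT rate.

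At an assumed 25% total rate of listed DLTs plus related grade 4 anaemia:
- all counted, p = 0.25: 0.422 + 0.178 = 0.600
- 0.5 point uncounted, p = 0.245: 0.611
- 1 point uncounted, p = 0.24: 0.622
- 3 points uncounted, p = 0.22: 0.665

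| Assumed total rate | Gain, 1 point uncounted | Gain, 3 points uncounted |
|---|---|---|
| 15% | 0.020 | 0.058 |
| 20% | 0.022 | 0.064 |
| 25% | 0.022 | 0.065 |
| 30% | 0.021 | 0.063 |
| 33% | 0.020 | 0.060 |

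At lower totals the gain for 1 point shrinks: 0.016 at 10% and 0.009 at 5%. Three points is the top of the 6.1.1 category for anaemia, where no grade is specified, so the last column overstates the effect if that category holds here. The rate in relapsed myeloma at 40-60 mg could be lower or higher. For scale only: with listed DLTs at 10% and independent related grade 4 anaemia at 5%, clearance would be 0.906 uncounted and 0.824 counted. The documents offer no basis for a rate that high.

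**The case against.** **On transfusion.** The intent of 5.11 is plain, its general sentence allows transfusion, Section 7.8 lets investigators deviate without prior IRB approval to remove an immediate hazard, and Section 12.2.3 gives the PI authority to settle disputes about deviations. A reader might infer that the protocol denies red cells to severely anaemic patients. The documents do not support that, because a clinician can act. What stands is that the transfusion would still be a deviation reportable within five days, under an instruction that should not depend on guessing what was meant.

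**On the DLT list.** The omission may be deliberate. Entry sets no haemoglobin floor, there is no anaemia row in Table 6.2.2, and erythropoietin and transfusion are supportive care; this fits treating anaemia in relapsed myeloma as something to manage rather than as dose-defining. That is a fair reading, though no rationale is stated, so the omission cannot be called an error outright. The grade 3 item lasting more than 7 days could also capture prolonged anaemia if its heading were ignored. The heading makes that the less natural reading, and an episode resolved within 7 days would escape anyway.

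The two points also pull against each other: quick recovery from grade 4 anaemia is least likely if red cells are withheld, and a long hold would usually count as a DLT. This narrows the gap mainly to an investigator who doses through the anaemia or resumes soon after transfusion.

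**On consequence.** Review by the Protocol Management Team, SAE reporting, removal for intolerance (5.8), the option to enrol up to six before escalating, and an RP2D below the MTD all help. They are discretionary, and none changes the DLT count.

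**Conclusion.** The 5.11 wording should be corrected. Followed exactly, it gives a result that was evidently not intended, and the remedy is one clause. The harm is softened, but not removed, by the hazard and dispute provisions.

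The DLT gap is real on the natural reading of 13.1 but has lower priority. A reader might conclude that anaemia can never be a DLT, or that the MTD will be materially too high. Neither follows: anaemia counts when it causes fewer than 21 doses or a cycle 1 beyond 35 days, and the likely effect on escalation is small, at about 0.02 in clearance probability per uncounted percentage point. That figure rests on assumed total rates of 15% to 33%, and on a level with 0/3 escalating without being filled to six. The actual rate of related grade 4 anaemia is not in the documents. The phase II sample size and error rates are not affected.

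**What to change.** 1. **Section 5.11.** State that the cycle 1 platelet thresholds apply to platelet transfusions only, and that red-cell transfusion is allowed as clinically needed and is recorded. Cost: a few words.

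2. **Section 13.1 (lower priority).** Add to the hematologic DLTs: *Grade 4 anaemia, at least possibly related to leflunomide and worse than the baseline grade.* Alternatively, state that anaemia is deliberately excluded, and why. The baseline qualifier is needed because entry sets no haemoglobin floor, although exclusion criterion 21 removes patients with current or planned transfusion support before treatment. Cost: one line and no new tests, since blood counts are already scheduled on days 1 and 14 of cycle 1. The downside is that an occasional disease-related anaemia judged possibly related may count as a DLT and slow escalation; the grade 4 threshold and the baseline qualifier limit this.

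3. **Optional.** Add a row to Table 6.2.2 for related grade 4 anaemia, with the hold and recovery criteria, including how transfusion is handled, set by the investigators. Grade 3 anaemia need not be a DLT.

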13.2 Evaluable Participants and Participant Replacement

All participants will be evaluable for toxicity from the time of their first treatment with leflunomide.

Evaluable for Dose-Escalation/De-Escalation Criteria: Participants will be considered evaluable for dose-escalation criteria if they receive at least 75% of leflunomide and are followed during cycle 1, or experience a DLT. All participants who are not evaluable for dose-escalation criteria will be replaced. Note: While patients who receive <75% of the intended dose of leflunomide will be considered unevaluable for determination of MTD, if a patient discontinues leflunomide due to toxicities prior to receiving 75% of the dose, the patient will be considered evaluable and will not be replaced.

Evaluable for Response: Participants will have their response classified according to the IMWG response criteria (See [Section 11](#)). All patients included in the study will be assessed for response to treatment, even if there are protocol treatment deviations or if the patient is later determined to be ineligible. Each patient will be assigned one of the following categories: 1) complete response (CR), 2) stringent complete response (sCR), 3) very good partial response (VGPR), 4) partial response (PR), 5) minimal response (MR), 6) stable disease (SD), 7) progressive disease (PD), 8) early death from malignant disease, 9) early death from toxicity, 10) early death due to other cause, or 11) unknown (not assessable, insufficient data).

All of the patients who met the eligibility criteria (with the possible exception of those who received no study medication) should be included in initial analysis of response rate; overall response (sCR/CR/VGPR or PR) and clinical benefit response (sCR/CR/VGPR/PR/MR or SD). Patients in response

categories 7-11 should be considered to have a treatment failure. Thus, an incorrect treatment schedule or incorrect drug administration does not result in the exclusion from the analysis of the response rate.

In addition, as part of the phase II anti-myeloma activity assessment, a sub-analysis will be performed where participants will be considered evaluable for response if they are confirmed eligible, receive at least 75% of leflunomide during the first cycle of therapy and have had their disease re-evaluated (phase II primary endpoint).

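### The Section 13.2 evaluability note has no attribution condition, so read literally it keeps as DLT-free a patient who stops early for a toxicity judged unrelated

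*Combined protocol and SAP*

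**What the plan says.** Section 13.1 defines a DLT as one of a list of toxicities that are "at least possibly related" "to leflunomide and occur during cycle 1". One listed criterion is any toxicity, or series of toxicities, resulting in "Fewer than 21 doses during cycle 1".

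Section 13.2 makes participants evaluable for escalation "if they receive at least 75% of leflunomide and are followed during cycle 1, or experience a DLT". It adds: "All participants who are not evaluable for dose-escalation criteria will be replaced". A note in the same paragraph then makes an exception to the 75% requirement: "if a patient discontinues leflunomide due to toxicities prior to receiving 75% of the dose, the patient will be considered evaluable". The note says that this patient is not replaced. It does not mention attribution, and it does not say that the patient counts as a DLT.

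Section 13.3.2 applies these counts. Its text allows escalation after three patients have finished cycle 1 with no DLT at the level. One DLT leads to expansion to six evaluable patients, and the MTD is the highest dose with at most 1 DLT in 6. Table 13.3.2 is driven by the number of evaluable patients.

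**The concern.** A patient who stops well short of 75% for a toxicity judged unlikely related or unrelated has no DLT under Section 13.1. The general rule in Section 13.2 would replace that patient. The note, taken at its word, keeps the patient, who enters Table 13.3.2 as evaluable with zero DLTs.

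Decisions rest on three to six patients per level. A patient seen for only part of the intended exposure has had less chance to show a DLT, so counting that course as tolerated shifts the rule toward escalation and never away from it.

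**Working it through.** **1. Do the two thresholds coincide?** Section 5.2 states: "The planned cycle length is 28 days. Leflunomide will be taken orally once daily". So 75% of cycle 1 is 0.75 × 28 = 21 doses, the same figure as the DLT criterion in Section 13.1.

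If 75% is instead counted in mg, with the three 100 mg loading doses (Section 5.5.1), the cycle total is 300 + 25 × d mg for daily dose d. The 75% mark is then reached at these dose numbers:

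| Daily dose (mg) | 10 | 20 | 30 | 40 | 50 | 60 |
|---|---|---|---|---|---|---|
| Dose number reaching 75% | 15 | 18 | 20 | 20 | 21 | 21 |

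On either count, a stop before 75% means fewer than 21 doses, unless the dose was reduced earlier in the cycle.

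**2. What does the note add?** A related toxicity that causes such a stop is a DLT, and the patient is already evaluable through the DLT clause of the general rule. Apart from the dose-reduction case, the only patients whose status the note changes are those whose toxicity was judged unlikely related or unrelated.

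**3. Can such stops occur?** Several hematologic, gastrointestinal and hepatic rows of Table 6.2.2 call for permanent discontinuation without an attribution condition. Section 3.1 admits patients with platelets of 50,000/µL and ANC of 1000/mm³, so an early cytopenia attributed to the disease is plausible.

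**4. Effect of one such patient (upper bound).** Let p be the true DLT rate and q = 1 − p. Give the early stopper zero DLT risk. The documents state no value for p, so a range is shown.

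- Escalation under the full rule (0/3, or 1/3 followed by 0/3): q³ + 3pq² × q³.
- The same with one early stopper among the first three: q² + 2pq × q³.
- At most 1 DLT in 6: q⁶ + 6pq⁵. With five truly at risk: q⁵ + 5pq⁴.

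At p = 1/3:

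- Escalation, all at risk: 0.296 + 0.132 = 0.428.
- Escalation, one early stopper: 0.444 + 0.132 = 0.576.
- At most 1/6, six at risk: 0.088 + 0.263 = 0.351.
- At most 1/6, five at risk: 0.132 + 0.329 = 0.461.

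| p | P(escalate), all at risk | One early stopper in first three | P(at most 1/6), six at risk | Five at risk |
|---|---|---|---|---|
| 0.20 | 0.709 | 0.804 | 0.655 | 0.737 |
| 0.30 | 0.494 | 0.634 | 0.420 | 0.528 |
| 1/3 | 0.428 | 0.576 | 0.351 | 0.461 |
| 0.40 | 0.309 | 0.464 | 0.233 | 0.337 |

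**5. Averaged over an assumed frequency.** Let u be the chance per patient of an unrelated early stop. If stoppers are kept with zero DLT risk, the effective DLT rate is p(1 − u). At p = 0.30:

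| u | p(1 − u) | P(escalate) |
|---|---|---|
| 0 (stoppers replaced) | 0.300 | 0.494 |
| 5% | 0.285 | 0.525 |
| 10% | 0.270 | 0.557 |
| 20% | 0.240 | 0.622 |

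**The case against.** The strongest reply is that the note only restates the 21-dose DLT. Its wording tracks that criterion, the thresholds are identical, and its purpose may be conservative: to stop a toxicity-driven early stop from being set aside as under-dosing. That reading is possible, but the text does not secure it. Table 6.2.2 has a heading for toxicities considered unrelated to the study agent, and both Section 6.2.1 and Section 13.1 add the relatedness condition where they intend it.

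Other text limits the problem, and these points stand:

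- Section 13.3.2 speaks of patients who have finished cycle 1, which points toward replacement, although its table counts evaluable patients.
- Attribution is broad. Section 7.6 classes an event as possible if it may be related, and Section 6.1.1 lists cytopenias, hepatic and gastrointestinal events as expected. Many early toxicity stops would therefore be DLTs. For other non-hematologic events judged unrelated, Table 6.2.2 maintains treatment by default.
- Zero DLT risk is a worst case. Three loading doses give 300 of 800 mg (37.5%) at the 20 mg level and 300 of 1800 mg (16.7%) at 60 mg. The metabolite half-life is about two weeks, although Section 5.7 calls for cholestyramine elimination after stopping. The note also covers patients who stop only just short of 75%.
- Escalation after 0/3 is optional, up to six patients may be treated at a level, and the RP2D may be set below the MTD.

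A reader might infer that the note contradicts the general rule. It does not: it is worded as an exception to the 75% requirement, and what it lacks is a qualifier. A reader might also take the chance of 0/3 (0.30 rising to 0.44 at p = 1/3) as the chance of escalating. That omits the route through 1/3 and expansion to six.

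**Conclusion.** The point holds as a gap in wording with a one-sided effect. Read literally, the note keeps as evaluable, DLT-free and not replaced a patient who stops before 75% for a toxicity judged unlikely related or unrelated. Related early stops are already DLTs and do not ease escalation.

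The step 4 figures are upper bounds, conditional on one such patient being present. The step 5 range rests on assumed frequencies as well as an assumed DLT rate. The documents give neither quantity, so they do not support the broader inference that escalation in this trial is too easy overall. They support only that this clause can ease it and cannot tighten it. That is worth correcting before dose decisions depend on an interpretation, but it does not undermine the phase I design.

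**What to change.** Reconcile the note with Sections 13.1 and 13.3.2:

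- Limit the note to toxicities at least possibly related to leflunomide, and say that these patients are counted as DLTs under the 21-dose criterion.
- State that a patient below 75% of dose without a DLT is not evaluable for escalation and is replaced, whatever the reason for stopping.
- State whether 75% is counted in doses or in mg, and make the reference in Section 13.3.2 to finishing cycle 1 agree with the evaluability definition used in Table 13.3.2.

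If the note was meant only to restate the 21-dose criterion, these words change nothing in practice. Otherwise the cost is an occasional extra replacement patient, within the six replacements that Section 13.4 already allows for, plus the accrual and cycle 1 observation time for that patient.
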